c Intervention Period includes study treatment and Active Follow-up and Survival Follow-up as defined in Section 4.4 (including for Safety Lead-in portion of the study). Day 0/Week 0 is considered the day of the first infusion of MT-401 (which differs from the Day 1 used for allogeneic HSCT). Each infusion and visit must be at least 2 weeks apart. Active Follow-up Period as defined in Section 4.4: occurs after the last dose of MT-401 has been administered until patient relapses/progresses or declines additional study visits. Timing of Follow-up Visits are in relation to the timing of the Day 0 visit. Sponsor will schedule Day 0 timing for all patients in all groups, including Group 1 SoC arm.

d SoC patients do not need to perform visit Weeks 2 or 4, unless clinically indicated. Week 0 visit for SoC patients may occur between days 85-130 post-HSCT, as instructed by Sponsor.

^e Survival follow-up begins after relapse/progression or active follow-up is completed and occurs every 3 months for 3 years, every 6 months for the remainder of the study (which can be phone contact to collect patient survival status [if alive, last date known alive, and if dead, date of death], and collect any additional anticancer therapy post-MT-401 or SoC received during study.

Confidential Page 19 of 74

f Brief physical exam, to include at a minimum, assessments of the Cardiovascular, Respiratory, and Gastrointestinal systems (height and weight will be needed at screening at minimum and any changes recorded if >10%).

g Pregnancy testing is required unless a patient has no possibility of being pregnant (for example post-hysterectomy). Perform as clinically indicated during intervention period for WOCBP. See Section 8.3.5 for details.

^h On day of MT-401 administration, laboratory assessments and/or disease assessments are completed prior to infusion (see Section 8.2.3 for additional details of laboratory assessments to be performed).

¹ Vital signs obtained within 1 hour pre- and post-infusion (window ± 15 min).

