^j Disease assessment will be performed on blood, bone marrow samples, and/or other tissue samples at these time-points. For Group 1 and Group 2, the screening disease assessment may be performed as part of SoC (prior to consent if it was already completed). For Group 1, pre-transplant testing of MRD should be performed locally by any testing methodology and results recorded in the eCRF. Post-transplant baseline MRD testing will be performed centrally, and results must be available prior to randomization. If any additional disease assessments, such as additional time points or additional testing (e.g., imaging for extramedullary disease), or visits occur due to clinical necessity, information will be recorded on eCRF. Includes central testing for MRD status for all samples collected as per SoC and as per standard institutional guidelines at other time points by methods outlined in protocol in Section 4.1 (samples stored for central confirmation at later date). If imaging is performed on a patient, the Sponsor may request imaging to be sent to a central vendor along with any disease assessment reports.

Disease assessment at Day 0 for Group 1 only (disease assessment does not need to be repeated if within 3 weeks of prior disease assessment and results can be pending prior to treatment).

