7. DISCONTINUATION OF MT-401 AND PARTICIPANT DISCONTINUATION/WITHDRAWAL

7.1. Discontinuation of MT-401

If it becomes necessary for a patient to permanently discontinue MT-401, the patient will remain in the study to be evaluated for safety, response, and survival. See the SoA (Table 1) for data to be collected at the time of intervention discontinuation and follow-up and for any further evaluations that need to be completed.

The following criteria will result in the patient being ineligible for further treatment on the protocol, although safety and response data will continue to be collected as applicable:

- Any patient who develops a DLT. In such patients, the toxicity will be followed until resolution or until their off-study date.
- Any patient who receives any other hematopoietic cell product (e.g., donor leukocyte infusion) except for routine blood product transfusions such as platelets and packed red blood cells. In such patients, AE data collection will cease.
- Any patient who enrolls in another clinical study involving investigational product or other type of medical research judged not to be scientifically/medically compatible with this study or receives antineoplastic treatment for relapse of their primary malignancy within 4 weeks after the T cell infusion. In such patients, adverse event data collection will cease.
- Refusal of the patient to continue treatment or observations.
- Decision by the investigator that discontinuation of treatment is in the patient's best medical interest
- Unrelated medical illness or complication deemed significant by the investigator.

• Death.

Confidential Page 41 of 74

- Progressive Disease.
- Lost to follow-up.
- At the request of Marker Therapeutics, Inc.
- Any patient who becomes pregnant.

Any new clinically relevant finding should be reported as an AE.

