6.4.1.2 Primary Efficacy Variables

Phase 2 Adjuvant (Group 1):

- RFS: defined as the time between the date of randomization and the date of first relapse per ELN recommendations or death by any cause, whichever occurs first. Relapse includes either hematologic and/or molecular relapse as defined in [Table 2](#) at any disease assessment. In the event that no relapse or death is documented prior to analysis cutoff or the start of new anti-cancer therapy, RFS will be censored on the date of the last evaluable disease assessment demonstrating no relapse prior to analysis cutoff or the start of new therapy. For patients who remain alive and have no baseline disease assessment or have no post-randomization disease assessment, RFS will be censored on the date of randomization. In addition, if relapse or death occurs after extended time without disease assessments, RFS will be censored on the date of the last evaluable disease assessment prior to the missed disease assessments.

For patients with relapse or death, a variable will be created to flag whether the earlier date of relapse or death occurs after extended time without disease assessments. The extended time is defined as below:

- Time from randomization date to Day 0 visit + 12 weeks + assessment window of 2 weeks, if the latest assessment prior to the event (relapse or death, whichever is earlier) \leq randomization date + 0.5*time from randomization date to Day 0 visit. For patients without Day 0 visit, an artificial Day 0 visit will be derived as randomization date + mean time from randomization date to Day 0 visit date in MT-401 arm, for analysis purpose only.
- 24 weeks + assessment window of 2 weeks, if the latest assessment prior to the event (relapse or death, whichever is earlier) \leq Day 0 visit + 6 weeks & $>$ randomization date + 0.5*time from randomization date to Day 0 visit
- 38 weeks + assessment window of 5 weeks, if the latest assessment prior to the event (relapse or death, whichever is earlier) \leq Day 0 visit + 18 weeks & $>$ Day 0 visit + 6 weeks
- 78 weeks + assessment window of 5 weeks, if the latest assessment prior to the event (relapse or death, whichever is earlier) \leq Day 0 visit + 37 weeks & $>$ Day 0 visit + 18 weeks
- 104 weeks + assessment window of 5 weeks, if the latest assessment prior to the event (relapse or death, whichever is earlier) \leq Day 0 visit + 78 weeks & $>$ Day 0 visit + 37 weeks

Phase 2 Active Disease (Group 2):

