7.2 Analysis Populations

The analysis populations are defined as follows:

- All Treated Patients: Includes all patients who received at least one dose of MT-401 or were randomized to SOC.
- All Randomized Patients: Includes all patients in Group 1 who were randomized with final dose and manufacturing process and are MRD⁻ prior to randomization by central testing and local testing, if a local test was also performed. A patient randomized based on negative MRD result per central test but confirmed to be MRD⁺ will be excluded from Group 1 analysis.

When MRD testing occurs with different methodology (eg, flow cytometry and PCR), the patient is considered MRD⁺ if either test detects MRD. If adjudication occurs between central testing and local testing for the same type of testing (eg, flow by central testing and flow by local testing), the final adjudicated result will be taken into account for the confirmed MRD result. A patient confirmed to be MRD⁺ prior to randomization will be excluded from Group 1 and will be included in Group 2 analysis if treated with MT-401.

- Per-Protocol (PP) Population: Includes all treated patients, as defined above, who have no major protocol deviations. If there is <5% difference in the all randomized patient population and the PP population for Group 1, no analyses will be performed on the PP population.

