The primary endpoint of RFS for Group 1 will be tested at $\alpha = 0.05$ (two-sided) at the final analysis. The analysis of RFS at the interim analysis will be performed for the purposes of testing for futility and possible re-estimation of sample size as described in [Section 7.4.7.3](#). Analysis at the interim and final analysis will be performed based on ([Chen et al. 2004](#)) in order to maintain the type 1 error at $\alpha = 0.05$ for RFS at the final analysis.

Secondary endpoints for Group 1, OS and GRFS, will be presented for descriptive purposes only and no adjustments will be made for multiplicity.

The primary endpoint of CR for Group 2 will be tested at $\alpha = 0.05$ (two-sided) at the final analysis. DOCR will be presented for descriptive purposes only and no adjustments will be made for multiplicity.

7.4.7.6 *Use of an “Efficacy Subset” of Patients*

The primary efficacy analysis for Group 1 will be performed on all randomized patients and the PP population will be utilized as a sensitivity analysis. The PP population will exclude patients received less than two-thirds of total planned dose or had other major protocol deviations.

7.4.7.7 *Examination of Subgroups*

Subgroup analyses may be conducted based on, but not limited to, the covariates defined in [Section 7.4.7.1](#).

For time to event endpoints forest plots of the event-free rates at landmark times may be generated to display the outcomes in subgroups. Additionally, Kaplan-Meier plots with subgroup KM curves overlaid on the same plot may be presented. For binary endpoints, the rates within subgroups may be presented in forest plots.

7.5 **Safety Evaluation**

Safety analysis will be carried out for the all treated patients population, to include all patients who receive at least one dose of study drug. Patients who do not complete the study, for whatever reason, will have all available data up until the time of termination included in the analysis. For safety analysis presented by study visit, the baseline value will be defined as the last value reported prior to first study drug administration.

7.5.1 *Extent of Exposure*

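### The Group 1 per-protocol set filters on dosing in Arm A only, and the SAP's expected total of 150 x 10^6 cells conflicts with the Phase 2 dosing passages

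*SAP*

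**What the plan says.** **Analysis sets.** SAP 7.2 defines the PP set thus: "Includes all treated patients, as defined above, who have no major protocol deviations". The treated set it starts from reads: "Includes all patients who received at least one dose of MT-401 or were randomized to SOC". Protocol Table 8 uses the same construction. SAP 7.4.7.6 makes PP the sensitivity analysis for the primary RFS result and adds: "The PP population will exclude patients received less than two-thirds of total planned dose or had other major protocol deviations". SAP 7.2 also has a skip rule for the PP set: "If there is <5% difference in the all randomized patient population and the PP population for Group 1, no analyses will be performed".

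**Time origin and dosing.** SAP 6.4.1.2 counts RFS from randomisation in both arms and treats the Day 0 visit as later: "For patients without Day 0 visit, an artificial Day 0 visit will be derived as randomization date" plus the mean gap seen in the MT-401 arm. Protocol Table 1, footnote c: "Sponsor will schedule Day 0 timing for all patients in all groups, including Group 1 SoC arm". Footnote d places the SoC Week 0 visit at days 85-130 after transplant. The baseline disease assessment is at about Day 80, before randomisation (Protocol 6.3). On the Day 0 assessment, Table 1 says: "disease assessment does not need to be repeated if within 3 weeks of prior disease assessment and results can be pending prior to treatment".

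**Stopping.** Protocol 7.1 opens its list with "The following criteria will result in the patient being ineligible for further treatment on the protocol". The list includes death and progressive disease. Protocol Table 6 defines progressive disease separately from haematologic and molecular relapse.

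**Planned dose.** SAP 7.4.3 takes expected dose as the sum of the three planned doses, gives that sum as 150 x 10^6 cells, and splits patients at 66.6% compliance. Protocol 4.3.2 and SAP 6.1 describe 100 x 10^6 cells per dose for Phase 2. Protocol 4.3.3 and SAP 6.3.1 allow a switch to 200 x 10^6.

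**The concern.** An Arm A patient must stay in the trial long enough to be infused in order to enter the PP set. An Arm B patient enters at randomisation. If a patient whose failure is detected early is not dosed, or not dosed again, the Arm A failure disappears and the comparable Arm B failure is kept. Agreement between the PP and primary results would then reassure less than it appears to.

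The PP set is also not defined as a subset of All Randomized. The exclusion of patients confirmed MRD-positive does reach it, but the final-product condition is not carried over.

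The 150 x 10^6 figure matters for two reasons. Applied to Phase 2, it makes the compliance table uninformative. And SAP 7.4.7.6 does not say which total its two-thirds cut uses, so whether PP entry takes one infusion or two is left open.

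**Working it through.** **1. Dose total.** Compliance = dose received / expected dose x 100. The figure of 150 reproduces as 3 x 50, which is the Safety Lead-in and the contingent Cohort -IV (Protocol Table 4). The Phase 2 passages give 3 x 100 = 300, or 3 x 200 = 600 after a switch.

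| Received (10^6 cells) | Against 150 | Against own planned total |
|---|---|---|
| One infusion of 100 | 66.7% | 33.3% (of 300) |
| Three of 100 | 200% | 100% |
| One infusion of 200 | 133.3% | 33.3% (of 600) |
| Three of 200 | 400% | 100% |

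Two-thirds of 150 is 100, so one 100 x 10^6 infusion passes. Two-thirds of 300 is 200 and of 600 is 400, so two infusions are needed.

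**2. Design inputs.** SAP 7.6 gives a control median of 8 months, 75 patients per arm, 50-month uniform accrual, 90 events and a hazard ratio of 0.55. Schoenfeld's formula gives 88 events for 80% power, and 80.9% power at 90 events, so the plan's figure reproduces.

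**3. Early events.** The exponential hazard is ln 2 / 8 = 0.0866 per month. P(event within d days) = 1 - exp(-0.0866 x d / 30.44). The table takes every patient at one gap, detection at once, no dose after an event, and no true effect.

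| Gap (days) | Expected events among 75 | PP hazard ratio | p<0.05 favouring MT-401 (nominal 2.5%) |
|---|---|---|---|
| 5 | 1.1 | 0.98 | 3.2% |
| 20 | 4.2 | 0.92 | 5.9% |
| 30 | 6.1 | 0.88 | 7.8% |
| 50 | 9.9 | 0.82 | 13.1% |

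The documents give no gap. The bounds are 85 - 80 = 5 and 130 - 80 = 50 days.

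**4. Main simulation.** The gap is assumed uniform on 5-45 days, with the cut at the 90th detected event, a log-rank test, and no (further) dose after a detected event. In the visit-based rows, 25% or 50% of events are found between visits; the rest are dated at the next scheduled assessment. Day 0 results are taken as pending, so the first dose is still given. The second-dose filter applies only if the two-thirds cut uses a 300 or 600 total. The last two columns give the share of trials in which the skip rule lets PP run, counting event-related exclusions only.

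| Filter, detection | Dropped | HR | p<0.05 favouring MT-401 | PP run, of those randomised at the cut | PP run, of 150 |
|---|---|---|---|---|---|
| None | 0 | 1.00 | 2.5-2.7% | - | - |
| First dose, instant | 4.2 | 0.91 | 6.5% | 15% | about 5% |
| Second dose, instant | 6.4 | 0.86 | 10.1% | 50% | about 30% |
| First dose, visit-based (25%, 50%) | 1.1, 2.2 | 0.97, 0.95 | 3.4%, 4.5% | under 1% | under 1% |
| Second dose, visit-based (25%, 50%) | 4.3, 5.0 | 0.90, 0.89 | 6.6%, 7.9% | 14%, 24% | about 6%, 12% |

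The two run columns differ because only about 124 patients (instant) or 129-132 (visit-based) have been randomised when the 90th event is detected. Five per cent of 124 is 6.2; of 150 it is 7.5.

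Hand check: about 62 Arm A patients at a mean gap of 25 days give 62 x 0.069 = 4.3 first-dose exclusions. Adding 14 days gives 62 x 0.105 = 6.5 for the second dose. Both are close to the simulated 4.2 and 6.4.

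**5. Softer assumption.** If half of these patients are dosed anyway, the visit-based hazard ratios are 0.97-0.99 (first dose) and 0.94-0.95 (second dose).

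**6. Run and favourable together.** With instant detection and no true effect, PP is both run and significant for MT-401 in about 0.3-0.9% of trials (first dose) and 2.7-4.5% (second dose), depending on the denominator.

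**The case against.** The strongest reply is that little depends on this analysis. The primary analysis uses All Randomized, PP carries no decision rule, and SAP 7.4.1 lists each exclusion with its reason. The skip rule would often cancel PP when early failures are the only exclusions. All of this stands. But the rule compares set sizes and does not balance the arms: once other deviations take the difference past 5%, PP runs with the asymmetry intact.

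Second, SAP 7.4.4 already has a landmark analysis with the same condition in both arms. Read as the Day 0 visit, it partly covers the first-dose issue. SAP 7.1.5 sets Study Day 0 for Group 1 at randomisation, but a landmark there would exclude essentially nobody, so the visit is the natural reading. It does not reach the second dose and does not change the PP definition.

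Third, a reader might infer that the protocol stops dosing at any relapse, which would make the bias certain. The text does not support that. Protocol 7.1 names progressive disease and death, relapse is defined separately, and dosing may proceed with Day 0 results pending. The gap is also unstated, and a constant hazard straight after a negative central MRD test may overstate early events.

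Fourth, the rule in SAP 7.4.3 is sound and only its figure is out of line. Under-dosing remains visible in the disposition and exposure summaries (SAP 7.3.1 and 7.5.1). That is fair, but following the printed figure still gives a wrong Phase 2 compliance table.

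**Conclusion.** Both points hold on the text, at a severity between minor and should-fix, and both are confined to the PP sensitivity analysis and the compliance summary.

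The PP entry conditions differ between arms; that is certain. The lean towards MT-401 is conditional on dosing stopping after a detected failure, which for relapse, haematologic or molecular, is an assumption. Its size rests on the assumed gap, exponential RFS and the speed of detection. Under 5-45 days it runs from a hazard ratio of about 0.97 (first-dose filter, visit-based) to 0.86 (second-dose filter, instant), and nearer 1 if some patients are dosed regardless.

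The 150 x 10^6 total conflicts with the Phase 2 passages. It would be tempting to add the two faults together, but they do not add. If the two-thirds cut uses 150, the second-dose case does not arise at 100 or 200 x 10^6 per infusion. If it uses 300 or 600, the printed figure does not affect PP.

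A reader might also infer that the trial's type I error is inflated, or that the primary set needs redefining. Neither follows, because the primary RFS test does not use PP.

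**What to change.** **PP set.** For RFS, define PP as a subset of All Randomized. Apply any dose-related exclusion through one landmark, counted in days from randomisation and identical in both arms. Alternatively, report the dose-based PP result as not comparable between arms and rely on the symmetric landmark as the sensitivity check. State that the SAP 7.4.4 landmark uses the Day 0 visit.

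**Dose total.** Reconcile SAP 7.4.3 with Protocol 4.3.2 and 4.3.3 and SAP 6.3.1 by computing expected dose as the sum of the doses planned for that patient. State that the two-thirds cut in SAP 7.4.7.6 uses the same denominator.

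**Minor clarification.** Protocol Table 5, footnote c calls patients given a different dose unevaluable, while Protocol 6.6 calls them evaluable in a separate subgroup. The two should be reconciled.

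**Cost.** Wording and programming only; no new data. SAP section 4 has the plan finalised before the interim analysis, which is the natural time to make the change. The landmark loses events: at day 73, for example (the longest assumed gap of 45 days plus 28 days for three doses), it keeps about 67 of 90 with instant detection or 75-79 with visit-based detection, so that check is less precise. In return the null hazard ratio goes back to 1.00, with 2.5-2.6% of trials favouring MT-401. Day 73 rests on the assumed gap and should be reset from the real schedule.

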7.3 Study Patients

7.3.1 *Disposition of Patients*

Patient disposition will be summarized for all enrolled patients by study phase and cohort or treatment group. Summaries will include the number and percentage of patients in each analysis population, completing all 3 doses, reason for not completing all doses, completing the study, and discontinuing the study early by the primary reason for discontinuation. Descriptive statistics for actual and potential follow-up times will be included.

7.3.2 *Protocol Deviations*

Important protocol violations will be summarized by study phase and cohort or treatment group and over all patients combined for all enrolled patients. Important protocol violations are protocol

deviations captured on-study that are deemed by the Sponsor to potentially impact the efficacy or safety conclusions of the study.

All important protocol violations will be determined and appropriately categorized prior to database lock. The number and percentage of patients with any important protocol violations as well as the number and percentage of patients with violations within each category will be presented.

7.4 Efficacy Evaluation

7.4.1 *Datasets Analyzed*

Efficacy analyses for Group 1 will be conducted in the all randomized patients population while efficacy analyses for Cohorts I-V and Group 2 will be conducted in the all treated patients population. Select efficacy analyses for Group 1 will be repeated in the PP population. A data listing of patients excluded from the PP Population, to include the reason for exclusion, will be presented.

7.4.2 *Demographic and Other Baseline Characteristics*

Demographic and baseline characteristics will include: age, sex, ethnicity, race, height, weight, and body mass index (BMI). Age will be calculated relative to date of informed consent, as follows:

- If the month and day portion of the informed consent date is prior to the month and day portion of the birthdate, age will be calculated as the year of informed consent minus the year of birth, minus one;
- If the month and day portion of the informed consent date is on or after the month and day portion of the birthdate, age will be calculated as the year of informed consent minus the year of birth.

BMI will be calculated as: weight (kg) / [height (cm) / 100]². Age, height, weight, and BMI will be summarized using descriptive statistics. Sex, age category (18-64 years, 65 years and above), ethnicity, and race will be summarized with the number and percentage of patients in each parameter category.

Disease history characteristics include: time since initial diagnosis (months), WHO classification, type of AML (secondary or treatment-related AML, de novo AML), disease status at screening, disease status at baseline, bone marrow blast percentage at baseline (for Cohort I-V and Group 2) complete remission prior to transplant (CR1/CR2/CR3; for Group 1 only), prior stem cell transplant (yes/no), time from transplant to randomization/first dose, time from first post-transplant relapse to first dose (for Cohort I-V and Group 2), history of post-transplant chronic GVHD (yes/no), maximum grade of chronic GVHD, history of post-transplant acute GVHD (yes/no), maximum grade of acute GVHD, type of transplant donor, conditioning regimen, MRD status pre- and post-transplant, genetic mutations identified, disease risk classification (favorable,

intermediate, unfavorable), present genetic abnormalities, bridging therapy (yes/no), number of lines of prior systemic therapy, prior cell therapy, and prior radiation therapy. Detailed summary of prior anti-cancer therapy will be provided for prior systemic therapy (excluding bridging therapy) and bridging therapy separately.

Demographic, baseline characteristics, and disease history characteristics will be summarized by study phase and cohort or treatment group for the all treated patients population. For Group 1, summaries will be repeated for the all randomized patients population and the PP population.

If an imbalance of more than 20% between the MT-401 and SOC arms is observed among the age, genetic mutations, transplant donor type, conditioning regimen, or complete remission status prior to transplant, the primary analysis may be modified to stratify for these factors.

Medical history data will be presented in patient data listings by study phase and patient.

7.4.3 *Measurements of Treatment Compliance*

Compliance to the study treatment regimen will be determined as the total dose received divided by the expected dose received, multiplied by 100. The total dose received will be calculated as the sum of actual dose received for each of the 3 planned doses. The expected dose received will be determined as the sum of the planned dose for each of the 3 doses (ie, 150×10^6 cells). Dosing compliance will be summarized using descriptive statistics, by study phase and cohort or treatment group, based on the all treated patients population. The number and percentages of patients who are < 66.6% compliant and \geq 66.6% compliant will be summarized.

7.4.4 *Primary Efficacy Endpoint Analysis Methods*

Phase 2 Adjuvant (Group 1):

The primary analysis of RFS will be performed when 90 RFS events have been observed. RFS curves will be estimated using the Kaplan-Meier (KM) product limit method. The KM estimate of the median, 25th and 75th percentiles will be reported, and their corresponding 95% CIs will be computed. KM estimates of RFS rates at milestone time points (ie, 3 month intervals) will be reported along with two-sided 95% CIs using Greenwood's formula, provided the minimum follow-up in patients exceeds the time point to support stable estimation of the rate. The hazard ratio and corresponding 95% CI will be estimated using a Cox proportional hazards model including a factor for randomized arm and stratification factors of pre-transplant MRD status (MRD⁺ vs. MRD⁻/Unknown) and cytogenetic risk (Unfavorable vs. Other). The treatment effect on RFS will be evaluated using a stratified log-rank test. The significance level to be used in the RFS analysis at the final analysis will be based on $\alpha=0.05$ (two-sided).

As noted in Section 7.4.2, if an imbalance of more than 20% between the MT-401 and SOC arms is observed among the age, genetic mutations, transplant donor type, conditioning regimen, or complete remission status prior to transplant, the primary analysis may be modified to stratify for these factors.

A landmark analysis will be performed including only patients who are relapse free, alive and have not withdrawn from the study by Day 0.

Phase 2 Active Disease (Group 2):

The CR rate and the corresponding 95% exact CI will be calculated. The number and percentages of patients in each best disease response category per ELN recommendations will also be presented. Results will be presented separately for Subgroups C and D. Data from a matched synthetic control arm may also be obtained and compared against the CR rate from Group 2 active disease patients as part of a separate statistical analysis plan.

The DOCR will be estimated using the KM product limit method and summarized similar to RFS as described above.

7.4.5 *Secondary Endpoint Analysis Methods*

Safety Lead-in (Cohorts I and II) and Cohorts III-V:

CR and DOCR will be summarized descriptively for active disease patients in the Safety Lead-in (Cohorts I and II) and Cohorts III-V similar to Group 2. Summaries will be presented by cohort and overall.

Phase 2 Adjuvant (Group 1):

The statistical methods for analyzing OS and GRFS for Group 1 patients are identical to those described for RFS.

Phase 2 Active Disease (Group 2):

The statistical methods for analyzing ORR for Group 2 are identical to those described for CR. For Group 2 active disease patients, DOR, PFS and OS will be estimated using the KM product limit method and summarized similar to RFS for Group 1 as described above. For Group 2 patients achieving CR following bridging therapy, RFS and GRFS will also be estimated using the KM product limit method as described above for Group 1.

7.4.6 *Additional Efficacy Endpoint Analysis Methods*

The analysis of markers of immune function, cell targeting, and signaling pathways will not be discussed in this SAP. If analyses of these endpoint are explored, they will be described in a separate analysis plan and may not be included in the primary CSR.

For Group 1 adjuvant patients, the time to MRD⁺ will be summarized similar to RFS, but with no statistical comparisons.

For Group 2 CR patients, the time to MRD⁻ will be summarized descriptively.

For Group 2 Subgroup D, among patients who had PCR detection of MRD at baseline, the percentage reduction from baseline will be summarized, as well as the number and percentage of patients whose disease level reduced by 50% or more.

A summary of PRO data will be presented using descriptive statistics for Group 2 only.

7.4.7 *Statistical/Analytical Issues*

7.4.7.1 *Adjustments for Covariates*

The planned primary analysis models will include adjustments for stratification factors of pre-transplant MRD status and cytogenetic risk. Subgroup analysis and/or analyses including additional factors may be conducted based on, but not limited to, the following covariates:

- Age (18-64 years, 65 years and above)
- Genetic mutations
- Transplant donor type (matched sibling, matched unrelated, haploidentical)
- Conditioning regimen (myeloablative, reduced intensity/nonmyeloablative)
- Complete remission status prior to transplant (CR1, CR2, CR3)

For time to event endpoints forest plots of the event-free rates at landmark times may be generated to display the outcomes in subgroups. Additionally, Kaplan-Meier plots with subgroup KM curves overlaid on the same plot may be presented. For binary endpoints, the rates within subgroups may be presented in forest plots.

Subgroup analyses are described in Section 7.4.7.7. In addition, data may be analyzed post-hoc to explore the effects of various factors. Such analyses will be labeled as post-hoc.

7.4.7.2 *Handling of Dropouts or Missing Data*

Patients with no post-baseline disease assessment will be included in the denominator for calculation of CR and ORR and will be treated as non-responders.

For time to event endpoints (RFS, OS, GRFS, PFS), patients with no baseline disease assessment or no post-baseline disease assessment will be censored using a censored value of 1 day.

No other imputations of missing data will be made.

7.4.7.3 *Interim Analyses and Data Monitoring*

A Sponsor review committee (SRC) will be convened to review the toxicities and endpoints related to the Safety Lead-in (Cohorts I and II), meet separately once Cohort III is complete and again once Cohorts IV-V are complete. The SRC will consist of at least 1-2 clinicians that includes the Medical Monitor and/or the Medical Director, along with 1 statistician.

Safety data will be reviewed at the end of the Safety Lead-in to determine if it is appropriate to move forward with the specific peptide manufacturer in the Phase 2 portion of the study. The evaluation of DLTs will be conducted in the DLT-evaluable set. Safety data will also be reviewed at the end of Cohort III to determine if it is appropriate to switch to a higher dose in the Phase 2 portion of the study. Additionally, safety data will also be reviewed at the end of Cohorts IV and V to determine if it is appropriate to switch to a dosing regimen with the MT-401 product manufactured using the accelerated process in the Phase 2 portion of the study. This decision will be made by the Sponsor based on multiple parameters, including the safety and biomarker data available.

A DMC will be formed for the Phase 2 portion of the study. The DMC will make recommendations on ongoing study conduct, including the accrual of additional patients to Group 1 based on the futility and efficacy criteria outlined below and any additional criteria established in the DMC charter. In addition, an Independent Efficacy Review Committee (IERC) may be formed to provide independent disease assessment. Separate charters will outline the details, including roles and responsibilities of these two committees.

Two formal interim analyses are planned during Phase 2, one for Group 1 and one for Group 2.

The interim analysis for Group 1 will occur when 45 RFS events have occurred. It is anticipated that this will occur approximately 30 months after the first patient randomized. At this analysis, the DMC will assess safety, futility, and potential expansion of study accrual. At the time of this analysis, enrollment of the remaining patients will continue, unless any safety concerns are identified.

The following options for the Group 1 interim analysis will be considered:

- Option 1: Terminate Group 1 due to futility if the RFS hazard ratio for MT-401:SOC is larger than 1.1 at the interim analysis. This futility stopping rule will be non-binding and can be overridden by the DMC and/or Marker.
- Option 2: Retain the planned target number for patient accrual and planned 90 RFS events if the conditional power (CP) calculated at the interim analysis is greater than 80% or less than 50% and the futility stopping rule is not met.
- Option 3: Increase the target number of planned accrual and RFS events if CP is between 50% and 80% and the futility stopping rule is not met. The target number of RFS events will be increased to achieve CP of 80% or increase by 50%, whichever is smaller. Target enrollment adjustments will be accomplished based on pooled event accumulation rate and a reasonable study duration projected via simulation.

The interim analysis for Group 2 will occur after the first approximately 10 patients in each subgroup have progressed or had the opportunity to be followed for 6 months. Clinical safety and efficacy will be reviewed comprehensively. Further enrollment for a subgroup may be terminated due to futility based on totality of the data. Patients treated in Cohorts IV-V with the same

manufacturing process as Group 2 may be included in Group 2 Subgroup C or Subgroup D analyses for decision making.

7.4.7.4 *Multicenter Studies*

This is a multicenter study, with approximately 20-25 study centers expected to participate. Efficacy data collected from all study centers will be pooled for data analysis. The effect of study center on the efficacy analysis results may be explored post-hoc, as needed.

7.4.7.5 *Multiple Comparisons/Multiplicity*

The primary endpoint of RFS for Group 1 will be tested at $\alpha = 0.05$ (two-sided) at the final analysis. The analysis of RFS at the interim analysis will be performed for the purposes of testing for futility and possible re-estimation of sample size as described in [Section 7.4.7.3](#). Analysis at the interim and final analysis will be performed based on ([Chen et al. 2004](#)) in order to maintain the type 1 error at $\alpha = 0.05$ for RFS at the final analysis.

Secondary endpoints for Group 1, OS and GRFS, will be presented for descriptive purposes only and no adjustments will be made for multiplicity.

The primary endpoint of CR for Group 2 will be tested at $\alpha = 0.05$ (two-sided) at the final analysis. DOCR will be presented for descriptive purposes only and no adjustments will be made for multiplicity.

7.4.7.6 *Use of an “Efficacy Subset” of Patients*

The primary efficacy analysis for Group 1 will be performed on all randomized patients and the PP population will be utilized as a sensitivity analysis. The PP population will exclude patients received less than two-thirds of total planned dose or had other major protocol deviations.

7.4.7.7 *Examination of Subgroups*

Subgroup analyses may be conducted based on, but not limited to, the covariates defined in [Section 7.4.7.1](#).

For time to event endpoints forest plots of the event-free rates at landmark times may be generated to display the outcomes in subgroups. Additionally, Kaplan-Meier plots with subgroup KM curves overlaid on the same plot may be presented. For binary endpoints, the rates within subgroups may be presented in forest plots.

7.5 **Safety Evaluation**

Safety analysis will be carried out for the all treated patients population, to include all patients who receive at least one dose of study drug. Patients who do not complete the study, for whatever reason, will have all available data up until the time of termination included in the analysis. For safety analysis presented by study visit, the baseline value will be defined as the last value reported prior to first study drug administration.

7.5.1 *Extent of Exposure*

